8.5 PACKAGING AND LABELING

The randomized labelled treatment box will contain:

- 1 randomized blinded labelled wallet with 6 or 8 capsules of FQ (5, 30, 100 or/and 200 mg or placebo) depending on the treatment arm and the weight band,
- An open label individual sachet containing sucrose granules for FQ oral suspension only in kits of weight band <35 kg,
- An open label individual sachet containing OZ439 + TPGS granules for oral suspension (150, 200, 300, 400, 600 or 800 mg) depending on the treatment arm and the weight band,
- An open label individual sachet containing sucrose granule for OZ439 oral suspension.

Packaging is in accordance with the administration schedule. The content of the labeling is in accordance with the local regulatory specifications and requirements.

8.6 STORAGE CONDITIONS AND SHELF LIFE

Investigators or other authorized persons (eg, pharmacists) are responsible for storing the IMP in a secure and safe place in accordance with local regulations, labeling specifications, policies, and procedures.

Control of IMP storage conditions, especially control of temperature (eg, refrigerated storage) and information on in-use stability and instructions for handling the Sanofi compound should be managed according to the rules provided by the Sponsor.

8.7 RESPONSIBILITIES

The Investigator, the hospital pharmacist, or other personnel allowed to store and dispense the IMP will be responsible for ensuring that the IMP used in the clinical trial is securely maintained as specified by the Sponsor and in accordance with applicable regulatory requirements.

All IMPs will be dispensed in accordance with the Investigator's prescription and it is the Investigator's responsibility to ensure that an accurate record of IMP issued and returned is maintained.

Any quality issue noticed with the receipt or use of an IMP (deficiency in condition, appearance, pertaining documentation, labeling, expiration date, etc) should be promptly notified to the Sponsor. Some deficiencies may be recorded through a complaint procedure.

A potential defect in the quality of IMP may be subject to initiation of a recall procedure by the Sponsor. In this case, the Investigator will be responsible for promptly addressing any request made by the Sponsor, in order to recall IMP and eliminate potential hazards.

Under no circumstances will the Investigator supply IMP to a third party, allow the IMP to be used other than as directed by this clinical trial protocol, or dispose of IMP in any other manner.

8.7.1 Treatment accountability and compliance

Measures taken to ensure and document treatment compliance and IMP accountability include:

- Proper recording of treatment kit number or packaging number as required on appropriate electronic case report form (e-CRF) page for accounting purposes.
- The unblinded pharmacist or designee will prepare the kit assigned by IVRS/IWRS, will complete the corresponding treatment log form, and will perform reconciliation by checking the consistency of the treatment number between IVRS/IWRS assignment notification, the treatment number printed on the kit boxes and the treatment log forms.
- IMP will also be recorded and tracked on the site IMP inventory forms.
- The monitor in charge of the study checks the data entered on the e-CRF by comparing them with the IMP that has been retrieved and the treatment log form.

8.7.2 Return and/or destruction of treatments

All partially-used or unused treatment boxes will be destroyed at study site or returned to the Sponsor for destruction according to local regulations.

A detailed treatment log of the destroyed IMP will be established with the Investigator (or the pharmacist) and countersigned by the Investigator and the monitoring team. The Investigator will not destroy the unused IMP unless the Sponsor provides written authorization.

8.8 CONCOMITANT MEDICATION

8.8.1 LIST OF FORBIDDEN CONCOMITANT MEDICATION

All drugs other than oral contraceptives, paracetamol (acetaminophen) at the maximum dose of 40 mg/kg/day, metoclopramide if repeated vomiting and beta-lactams for any infection needing an antibiotic treatment are prohibited over the entire study period unless medically justified. The dosage and number of dose(s) will be recorded. The use of other contraceptive methods may be discussed.

Traditional and herbal remedies are not permitted during the study.

8.9 RESCUE TREATMENT FOR MALARIA

The use of a rescue therapy is recommended in the following cases:

- Vomiting during or after FQ dosing or vomiting within 35 minutes after OZ439 re-dosing
- Treatment failure as-per protocol section “Classification of Treatment Outcomes”

The use of established anti-malarial drug combination per WHO recommendations (1) or local guidelines is to be considered as a rescue therapy and the choice of the best therapeutic option is left at Investigator’s decision.

In case of rescue therapy is given, where possible, a PK (OZ439 and FQ) sample should be taken before giving rescue therapy.

Before giving established ACT:

- Blood films and parasite genotyping must be taken for all patients.
- RT-PCR and qPCR for patients >5 years only.

Following administration of established ACT, patients should be managed according to local standard of care practices. Safety data should continue to be collected in the e-CRF, according to the study schedule, and up to the end of the study even if re-emergence is confirmed.

Patients who will have received a rescue treatment after the OZ439/FQ has failed will be part of the Per-Protocol Population (see [Section 11.3.2.2](#)) whereas patients who will have received a rescue treatment because of vomiting during IMP administration will be part of the safety analyses only.

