- a* At each patient visit/contact post dose, antimalarial rescue therapy conditions will be assessed and rescue therapy may be given accordingly.
- b* Discharge at 48 hours (African patients > 5 years) or 72 hours (all other patients) (or up to Day 7) depending on age, parasite and fever clearance, clinical judgment and patient convenience. If discharged prior to Day 7, will return to Investigational site for further assessment on all scheduled times up to Day 7.
- c* Patients should have fasted from food and milk for 3 hours before administration. Neither food nor milk should be taken within 2 hour after the end of IMP dosing.
- d* Blood films (thick and thin, performed locally) and temperature measurements need to be confirmed as follows: when 1st parasite clearance or 1st temperature <37.5 °C, measurements need to be confirmed with second reading 6 to 12 hours after the 1st measurement (ie, to determine Parasite Clearance or Fever Clearance). The first measurement (if confirmed) will be considered the 'Clearance Time'. Only asexual count will be used as parasitemia for evaluation of study endpoints. If parasites have not cleared by 72 hours after IMP administration and criteria for rescue medication are not met at 72 h, blood films should continue to be taken according to site standard practice (or at minimum every 8 hours) until parasite clearance is shown or until criteria for rescue medication are met (see [Section 8.9](#)). If these additional blood smears are taken they should be recorded as unscheduled visits in the CRF.
- Note: Axillary temperature should be recorded. If the axillary method is not possible, an alternative route (tympenic, oral, rectal) may be used. Within an individual patient the same method of temperature measure should be used throughout the study.
- e* Measurement required within 4 hours prior to dosing. Local thick and thin blood films performed at the site, before Informed Consent signature, according to local standard procedures, can be used as screening / Pre-dose parasitaemia assessments ([Section 9.3.1.1](#)) provided that a standard procedure is in place at site and blood films stainings are performed according to Study Parasitology Procedures Manual.

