8 STUDY TREATMENTS

8.1 INVESTIGATIONAL MEDICINAL PRODUCTS

The investigational medicinal products (IMPs) will be administered in the following order: FQ then OZ439.

All details regarding the preparation of IMPs, including suspension of FQ and OZ439, will be described in a separate pharmacy manual.

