8.1.4 Re-dosing in the event of vomiting after OZ439 administration

- If a patient vomits within 5 minutes of the start of dosing with OZ439, they can be re-dosed with a freshly prepared new suspension from a new individual patient treatment kit assigned via IVRS/IWRS. No re-dosing of FQ will be performed.
- If vomiting occurs from 5 minutes to 35 minutes post start of OZ439, they should continue to take the OZ439 dose (if any left), but should not be re-dosed.
- If a patient vomits after 35 minutes from the start of OZ439 dosing, they should not be re-dosed.
- No re-dosing of FQ will be performed if a patient vomits during or after FQ administration but before OZ439 administration. In that case, OZ439 will not be administered and the patient will receive a rescue therapy as per [Section 8.9](#).

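### The vomiting trigger for rescue in 8.9 omits the before-OZ439 limit used in 8.1.4, so read literally it covers all vomiting after OZ439

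*Protocol*

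**What the plan says.** Section 8.1 fixes the order of dosing: the products are "administered in the following order: FQ then OZ439".

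Section 8.1.4 deals with vomiting around dosing in four bullets:

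- Under 5 minutes: "If a patient vomits within 5 minutes of the start of dosing with OZ439, they can be re-dosed". FQ is not repeated.
- 5 to 35 minutes: "If vomiting occurs from 5 minutes to 35 minutes post start of OZ439, they should continue to take the OZ439 dose", without re-dosing.
- Later: "If a patient vomits after 35 minutes from the start of OZ439 dosing, they should not be re-dosed".
- Before OZ439: "No re-dosing of FQ will be performed if a patient vomits during or after FQ administration but before OZ439 administration". Here OZ439 is withheld and the patient goes to rescue, with a reference to 8.9.

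Section 8.9 lists when rescue is recommended. Its first bullet is "Vomiting during or after FQ dosing or vomiting within 35 minutes after OZ439 re-dosing"; its second is treatment failure. Its last paragraph keeps patients rescued after treatment failure in the per-protocol population. Patients rescued for vomiting while the study products were being given go to the safety analyses only.

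Three other places rely on these conditions. Footnote a to the flow chart (section 1.1) says "At each patient visit/contact post dose, antimalarial rescue therapy conditions will be assessed and rescue therapy may be given accordingly". Section 9.1.1 denies ACPR to a patient rescued under the 8.9 conditions. Section 11.3.2.1 removes from mITT those who needed rescue for vomiting during administration, with a reference to 8.9.

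**The concern.** Sections 8.1.4 and 8.9 describe the same event in almost the same terms, but only 8.1.4 limits it to the time before OZ439. The 8.9 trigger has no such limit and no end time. Given the dosing order, its literal wording takes in every vomiting episode after OZ439, whether minutes or days later.

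Section 8.9 is also the section to which 8.1.4, 9.1.1 and 11.3.2.1 refer. An over-broad trigger can therefore affect three things: whether a child receives an established antimalarial on top of the study treatment, whether that child is in the primary analysis, and whether the child counts as a responder. Two sites could handle the same child differently and both claim to follow the protocol. Vomiting is foreseeable here, since section 4.1 names it among the main adverse events reported in the earlier studies.

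**Working it through.** No arithmetic applies, because the plan states no figure on this point. The check sets each vomiting case under 8.1.4 beside 8.9 read literally.

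| Time of vomiting | 8.1.4 | 8.9, literal | Comparison |
|---|---|---|---|
| During or after FQ, before OZ439 | OZ439 withheld, rescue | Rescue recommended | Agree |
| Within 5 minutes of starting OZ439 | OZ439 may be re-dosed | Rescue recommended | Direct conflict |
| 5 to 35 minutes after starting OZ439 | Finish the dose, no re-dosing; silent on rescue | Rescue recommended | 8.9 goes further |
| More than 35 minutes after starting OZ439 | No re-dosing; silent on rescue | Rescue recommended, no end time | 8.9 goes further |
| Within 35 minutes after OZ439 re-dosing | Not addressed separately | Rescue recommended (second limb) | 8.9 adds a rule |

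**Which reading was meant.** Under 8.1.4 a patient is re-dosed with OZ439 only after vomiting within 5 minutes of starting it, and so always after FQ. If the first limb of 8.9 already covered that patient, rescue would have been recommended before any re-dosing, and the second limb would add nothing. The second limb has a purpose only if the first stops at the start of OZ439. With that limit restored, the conflict in the second row and the excess in the third and fourth rows disappear, and the last row stands as a separate trigger.

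**What follows if 8.9 is applied literally.** Take a child of 5 years or under in Africa, the population for the efficacy analyses.

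1. *Rescued for vomiting close to dosing.* OZ439 may be drunk over up to 30 minutes (8.1.2), so vomiting in that period can be called vomiting during administration. Under the last paragraph of 8.9 and under 11.3.2.1 the child may leave mITT. Per-protocol is a subset of mITT (11.3.2.2), so the child leaves that too.
2. *Rescued for vomiting hours later.* This is not clearly vomiting during administration, so the exclusion does not clearly apply. Nor has treatment failed, so the sentence that keeps failures in per-protocol does not describe the child either. If the child stays in mITT, 9.1.1 counts the rescue as non-ACPR.
3. *Same child at a site that follows 8.1.4.* No rescue is given. The child stays in and is classified on blood films and clinical course.

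The exclusion phrase in 8.9 and 11.3.2.1 is a looser description than either limb of the trigger. In particular, vomiting up to 35 minutes after a re-dose need not occur while a dose is being taken.

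**The case against.** The strongest reply is that the intent is plain. The re-dosing limb makes sense only under the 8.1.4 limit, and 8.1.4 is the specific rule and points to 8.9 for the one case it sends to rescue. Rescue is also only recommended in 8.9 and only permitted in the flow-chart footnote. This stands as to intent and keeps the point minor. It does not correct the text that sites use at the bedside.

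Four stronger readings are tempting, and the protocol does not support them:

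- *That 8.1.4 manages all vomiting after OZ439 without rescue.* It governs re-dosing. For vomiting at 5 minutes or later it is silent on rescue and does not forbid it. Only the case under 5 minutes conflicts directly.
- *That 8.8.1 confirms on-study management.* That section only lists "metoclopramide if repeated vomiting" among the permitted drugs. It does not say that rescue is withheld.
- *That every child rescued in this way leaves the primary analysis.* The exclusion reaches only rescue for vomiting during administration. Further per-protocol exclusions are left to the SAP.
- *That power suffers.* There is no vomiting rate from which to calculate a loss, and sections 11.1 and 11.5 continue recruitment to 150 evaluable patients per arm unless the arm is stopped for futility.

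A fair clinical point also remains. Narrowing 8.9 removes the default recommendation for a child who vomits soon after OZ439 and is not re-dosed, and who may be under-dosed. The sponsor may have wanted discretion there.

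**Conclusion.** The point holds as a wording defect with operational consequences. The first bullet of 8.9 lacks the limit that 8.1.4 carries. Taken literally it contradicts 8.1.4 for vomiting within 5 minutes of starting OZ439 and extends rescue beyond 8.1.4 for all later vomiting. Depending on timing, a child rescued on the literal reading may be excluded from mITT and per-protocol, or may count as non-ACPR without treatment failure. The second outcome is the more troublesome for the primary endpoint, because it records a failure that the drugs did not cause.

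The size cannot be given. It depends on how often children vomit after OZ439 and how many sites would apply 8.9 literally, and the protocol supplies neither. No stated power, sample size or decision rule changes. The conclusion rests on the fixed dosing order and on the text of the sections cited; the SAP is not at hand and may define the populations more closely. It is worth correcting but of low severity.

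**What to change.** In the first bullet of 8.9, limit the first limb to vomiting during or after FQ that happens before OZ439 is given, as 8.1.4 does. Keep the second limb (within 35 minutes after an OZ439 re-dose) unchanged. In the last paragraph of 8.9 and in 11.3.2.1, replace the general phrase about vomiting during administration with a reference to exactly these two cases. Rescues for vomiting then fall outside mITT and per-protocol by definition, and 9.1.1 can stay as it is.

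The cost is a few words in two sections and a clarification to sites, with no extra patients or data. The one downside is that rescue is no longer recommended by default for a child who vomits soon after OZ439 and is not re-dosed. That child remains covered by the treatment-failure bullet of 8.9 and by the scheduled monitoring, with blood films from 6 hours after dosing (10.1.2). If the sponsor wants investigator discretion for this child, 8.9 should say so and state how the child is analysed.

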9 ASSESSMENT OF INVESTIGATIONAL MEDICINAL PRODUCT

9.1 PRIMARY ENDPOINT

9.1.1 Primary efficacy endpoint

- PCR-adjusted ACPR at Day 28.
 - The ACPR is defined as a negative parasitemia (blood films) at Day 28, irrespective of axillary temperature, without previously meeting any criteria of early treatment failure (ETF) or late clinical failure (LCF) or late parasitological failure (LPF) or having received a rescue treatment for malaria in the conditions defined in [Section 8.9](#).
 - The PCR-adjusted ACPR applies only to recrudescence (re-emergence of the original clone of parasite that is present at baseline). Recrudescence is distinguished from re-infection by genotyping the parasite clone.

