11.3.2 Efficacy populations

Two efficacy analysis populations will be considered ie, Modified intent-to-treat (mITT) and Per-protocol (PP) populations focused on the “lower” NAI African population.

For the Asian patients and for the higher NAI population defined as all randomized patients >5 years in Africa (Cohort 1 & 2), with parasitologically confirmed malaria at baseline, who received at least the single administration OZ439/FQ, separate statistical reporting on all efficacy endpoints will be provided as secondary analyses.

The primary efficacy analysis population will be the per-protocol (PP) population defined as African patients of lower NAI; children ≤5 years in Africa (see [Section 11.3.2.2](#)).

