11.3.2.1 Modified intent-to-treat population

Modified intent-to-treat (mITT) population is defined as all randomized African patients of “lower” NAI population (ie defined as children ≤ 5 years in Africa) with parasitologically confirmed malaria at baseline, who received at least the single administration OZ439/FQ, ie, who did not need rescue therapy due to vomiting during IMP administration (see [Section 8.9](#)).

African patients with age >5 years old, and Asian patients will not belong to the mITT.

Patients in the mITT population will be analyzed according to the treatment arm allocated by randomization.

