11.3.2.2 Per-protocol (PP) population

Per-protocol (PP) population is defined as mITT patients who do not qualify for a major deviation, as defined in the statistical analysis plan.

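### Rescue for vomiting is a failure under the primary endpoint, but children rescued for vomiting during dosing are in neither efficacy population, so they cannot lower the Day 28 ACPR

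*Protocol*

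**What the plan says.** Section 9.1.1 defines ACPR as a negative film at Day 28 without earlier ETF, LCF or LPF, "or having received a rescue treatment for malaria in the conditions defined in" Section 8.9.

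Section 8.9 gives two conditions for rescue. The first is "Vomiting during or after FQ dosing or vomiting within 35 minutes after OZ439 re-dosing". The second begins "Treatment failure as-per protocol section" and points to the classification of treatment outcomes.

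The last paragraph of 8.9 assigns patients to analysis sets. Those rescued after the study drug failed belong to PP, whereas "patients who will have received a rescue treatment because of vomiting during IMP administration will be part of the safety analyses only".

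Section 11.3.2.1 builds the same exclusion into mITT, which is limited to children "who did not need rescue therapy due to vomiting during IMP administration". Section 11.3.2.2 makes PP a subset: "Per-protocol (PP) population is defined as mITT patients who do not qualify for a major deviation". Section 11.3.2 states that "Two efficacy analysis populations will be considered ie, Modified intent-to-treat (mITT) and Per-protocol (PP) populations", both restricted to African children of 5 years or younger. Section 11.4.3 makes PP primary and adds an mITT analysis of the primary endpoint only if the two sets differ by more than 5%.

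**The concern.** The endpoint definition and the population definitions treat the same child differently. The ETF, LCF and LPF terms of ACPR already cover the treatment-failure condition in 8.9, so the separate rescue term matters essentially only for vomiting. Yet children rescued for vomiting during administration are removed before the endpoint is scored.

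This is an exclusion after randomisation, for an event that Section 4.1 names among the main adverse events of these drugs. Each arm is tested alone against a fixed 90%, so no comparison arm carries an offsetting loss. Leaving out children whom 9.1.1 would score as failures can only raise the observed ACPR. The study is meant to inform the choice of a Phase III dose, so the size of the effect in each arm matters.

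**Working it through.** **1. Follow the child through the text.**

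| Step | Section | Result for a child rescued for vomiting during administration |
|---|---|---|
| Endpoint | 9.1.1 with 8.9 | Not ACPR |
| Analysis-set rule | 8.9, last paragraph | Safety analyses only |
| mITT | 11.3.2.1 | Excluded |
| PP | 11.3.2.2 | Excluded, as a subset of mITT |
| mITT fallback | 11.4.3 | In neither set, so adds nothing to the difference and is not restored |

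**2. Compare the two wordings.** The rescue trigger covers vomiting during or after FQ, and vomiting within 35 minutes after OZ439 re-dosing. The exclusion covers vomiting during administration. Section 8.1.2 allows at most 30 minutes for drinking the suspension, so the 35-minute window can run past administration. A child rescued for vomiting after FQ, or after re-dosing, is excluded if administration is read broadly and is a failure if it is read literally.

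**3. Reproduce the planned power.** Inputs: n = 150, null rate 0.90, true rate 0.964 (Section 11.1); success if the Clopper-Pearson two-sided 95% lower limit exceeds 0.90 (Section 11.4.3.1). The lower limit for x successes in n is the 0.025 quantile of Beta(x, n − x + 1).
- 143/150 has lower limit 0.9062 and 142/150 has 0.8976, so success needs at least 143, that is, at most 7 failures.
- P(X ≥ 143) for Binomial(150, 0.964) = 0.825.
- With all four futility looks (Beta(9.5, 0.5) prior, stop if Pr(H0|data) ≥ 0.30; continue with at least 46/50, 69/75, 91/100 and 114/125) power is 0.817.

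Both agree with the stated figure of at least 80%. The sample size is not in error.

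**4. How many excluded children overturn a success?** With f failures among 150 PP children, add k excluded children as failures and find the smallest k for which the lower limit of (150 − f)/(150 + k) is no longer above 0.90.

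| f | PP result | Lower limit | k | With k added | Lower limit | k/(150 + k) |
|---|---|---|---|---|---|---|
| 0 | 150/150 | 0.976 | 9 | 150/159 | 0.8953 | 5.7% |
| 1 | 149/150 | 0.963 | 8 | 149/158 | 0.8946 | 5.1% |
| 2 | 148/150 | 0.953 | 7 | 148/157 | 0.8940 | 4.5% |
| 3 | 147/150 | 0.943 | 6 | 147/156 | 0.8933 | 3.8% |
| 4 | 146/150 | 0.933 | 5 | 146/155 | 0.8926 | 3.2% |
| 5 | 145/150 | 0.924 | 3 | 145/153 | 0.8996 | 2.0% |
| 6 | 144/150 | 0.915 | 2 | 144/152 | 0.8989 | 1.3% |
| 7 | 143/150 | 0.906 | 1 | 143/151 | 0.8983 | 0.7% |

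The true rate used for power implies about 150 × 0.036 = 5.4 failures, which is in the lower part of this table.

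**5. The same question before the data.** Let v be the rate of rescue for vomiting, which is not in the protocol. Assume ACPR is 96.4% in the other children and take 150 dosed children in all. ACPR counting these rescues as failures is 0.964(1 − v).

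| v (assumed) | ACPR, all dosed | Chance of success, with futility looks |
|---|---|---|
| 0% | 96.4% | 0.82 |
| 1% | 95.4% | 0.61 |
| 2% | 94.5% | 0.40 |
| 3% | 93.5% | 0.23 |
| 5% | 91.6% | 0.06 |

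ACPR reaches the null value of 90% at v = 1 − 0.90/0.964 = 6.6%.

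**The case against.** The exclusion is deliberate and disclosed: 8.9 and 11.3.2.1 agree and cross-refer. An endpoint definition says how to score an analysed patient, and a population definition says who is analysed, so the two can coexist with part of the rescue term idle. The exclusion also has a rationale. Under 8.1.4 a child who vomits FQ before OZ439 never receives OZ439 and is given another antimalarial, so the Day 28 result says little about the combination. Efficacy in children who retained the dose is a legitimate question for a Phase IIb study. All of this stands, and it is why PP can remain primary. It does not explain why the endpoint carries a term whose main content the populations remove, or settle the children caught between the two wordings.

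The excluded children are not hidden. They are in the safety population, their vomiting is tabulated by arm, and Section 11.3 gives population counts by arm against all randomised. Those tables do not, however, have to give the reason for leaving mITT or show the effect on ACPR.

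A supportive table is often left to the analysis plan, which is not at hand. The exclusion itself is fixed in the protocol, however, and the plan is left only the major deviations that separate PP from mITT.

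A reader might infer three stronger claims that the protocol does not support:
- **That the exclusion removes exactly the children whom the rescue term catches.** The trigger is wider than the exclusion.
- **That no child who loses the dose can lower ACPR.** Under 8.1.4, a child who vomits the first OZ439 dose from 5 minutes after its start is not re-dosed, and those bullets call for no rescue. If not rescued, that child stays in mITT, and in PP unless a major deviation applies, and can fail.
- **That the higher FQ arms are flattered.** That needs vomiting to rise with FQ dose, and no such trend is given. Exclusion criterion E 06 also keeps out children with severe vomiting at entry.

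**Conclusion.** The point holds in a limited form. Children rescued for vomiting during administration are failures by 9.1.1 but cannot lower ACPR in mITT or PP, and no efficacy analysis in the protocol brings them back. For children rescued for vomiting after FQ or after OZ439 re-dosing, the protocol leaves open whether they are failures or excluded.

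The possible size is large relative to the success rule. With 4 to 7 PP failures among 150, between 5 children and 1 child reverse the conclusion; even with no failures, 9 do. These counts follow from the protocol's own rule. How likely they are depends on a vomiting-rescue rate that the protocol does not give, so the 1% to 6% range and the power figures are sensitivity calculations, not forecasts. The planned sample size and power are sound for the population as defined.

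**What to change.** 1. Keep PP as the primary population.
2. Pre-specify, for each arm, a supportive Day 28 PCR-adjusted ACPR with exact 95% confidence interval. Base it on all randomised African children of 5 years or younger with confirmed malaria who received any part of the study drug, and count rescue for vomiting as failure.
3. Beside the primary result, report for each arm how many children were rescued for vomiting.
4. Before unblinding, reconcile Sections 8.1.4, 8.9, 9.1.1 and 11.3.2.1, so that the rescue term, the rescue trigger and the exclusion describe the same children, or state where they are meant to differ. This concerns analysis wording only; no dosing or rescue rule needs to change for it.

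The cost is one more table from dosing and rescue data already collected, and a wording change. The downside for the sponsor is a second figure that can only be equal or less favourable as far as these children are concerned.
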